 641 *Administered PTSD Scale for DSM-5 (CAPS-5)*. Interview available from the National Center for PTSD at
 642 www.ptsd.va.gov.

643 Weathers, F. W., Blake, D. D., Schnurr, P. P., Kaloupek, D. G., Marx, B. P., & Keane, T. M. (2013). *The Life Events*
 644 *Checklist for DSM-5 (LEC-5)*. Instrument available from the National Center for PTSD at www.ptsd.va.gov.

645 Weathers, F. W., Litz, B. T., Keane, T. M., Palmieri, P. A., Marx, B. P., & Schnurr, P. P. (2013). *The PTSD Checklist*
 646 *for DSM-5 (PCL-5)*. Instrument available from the National Center for PTSD at www.ptsd.va.gov.

647
 648 **12.0 TIME REQUIRED TO COMPLETE THE RESEARCH (including data analysis).** Approximately 3 years from the
 649 time participant recruitment starts.

650 13.0 STUDY CLOSURE PROCEDURES

653 At the completion of the study a protocol closure report will be submitted for review. At the time of study closure, all links
 654 between PHI and the study data will be destroyed unless the participant has also agreed to participation in the STRONG
 655 STAR Repository approved by the UTHSCSA IRB (HSC20100475H). Informed consent documents and the HIPAA
 656 authorizations will be kept for 6 years past the closure of the study IAW 32CFR219 and IAW 45 CFR160-164, before
 657 being destroyed.

658 14.0 Funding.

- 660 • The DoD to the Military Suicide Research Consortium at Florida State University managed by the
 661 Congressionally Directed Medical Research Program is funding this project.
- 662 • Florida State University then awarded a subcontract for this specific project to the Boston VA Research
 663 Institute (BVARI), PI: [name] PhD.

664 • BVARI in turn awarded a subcontract to UTHSCSA for this specific project, PI: [name].
665
666

667 **15.0 Description of Assessments:**

668
669
670

671 1. Supplemental Demographic Form_v1.0 : The Demographics Form queries eight standard demographics and
672 military service information not part of the Military Suicide Research Consortium (MSRC) Common
673 Demographics (e. g., height, weight, military grade, type of military service, etc.).
674
675
676
677
678
679
680
681
682
683
684
685
686
687
688
689
690
691
692
693
694
695
696
697
698
699
700
701
702
703
704
705
706
707
708
709
710
711
712
713
714
715
716
717
718
719
720
721

671 2. Military Suicide Research Consortium (MSRC) Common Demographics: The MSRC Common Demographics
672 (CDem) were developed by the MSRC. As a requirement of funding, the research team is required to administer
673 these questionnaire and upload a limited data set (with dates but without other patient identifiers) as a SPSS file
674 to the MSRC website. The MSRC Common Demographics is a 32 item self-report questionnaire compromised of
675 questions related to standard demographics (race, gender, age) and military service information (e.g., rank).
676
677
678
679
680
681
682
683
684
685
686
687
688
689
690
691
692
693
694
695
696
697
698
699
700
701
702
703
704
705
706
707
708
709
710
711
712
713
714
715
716
717
718
719
720
721

671 3. Military Suicide Research Consortium (MSRC) Common Data Elements: The MSRC Data Elements (CDEs)
672 were developed by the MSRC. As a requirement of funding, the research team is required to administer these
673 questionnaire and upload a limited data set (with dates but without other patient identifiers) as a SPSS file to the
674 MSRC website. The MSRC CDEs is a 91 item self-report questionnaire compromised of questions related to
675 self-injurious thoughts, behaviors and related psychopathology.
676
677
678
679
680
681
682
683
684
685
686
687
688
689
690
691
692
693
694
695
696
697
698
699
700
701
702
703
704
705
706
707
708
709
710
711
712
713
714
715
716
717
718
719
720
721

671 4. Health Interview: The original Health Care Utilization (HCU) is a 16-item questionnaire developed in 2000 for Dr.
672 Patricia A. Resick's NIH grant, "Cognitive Processes in PTSD: Treatment II." The questionnaire was based on
673 the 1999 Behavioral Risk Factor Surveillance System. The version that will be administered as part of the
674 STRONG STAR Consortium has been modified to be of increased relevance to active duty service personnel.
675 The measure includes items regarding use of mental health services, current psychiatric medication, past
676 psychiatric medication, hospitalization, and outpatient medical services, as well as items intended to assess
677 changes in participants' military status. Tobacco/nicotine use will also be queried.
678
679
680
681
682
683
684
685
686
687
688
689
690
691
692
693
694
695
696
697
698
699
700
701
702
703
704
705
706
707
708
709
710
711
712
713
714
715
716
717
718
719
720
721

671 5. Self-Injurious Thoughts and Behaviors Interview (SITBI): The SITBI (Nock, Holmberg, Photos, & Michel, 2007) is
672 a structured interview assessing the presence, frequency, and characteristics of self-injurious and suicidal
673 thoughts and behaviors. The SITBI will be administered by an Independent Evaluator, who will instruct the
674 participants to answer the questions based on their entire lifetime of experience. The SITBI has shown high
675 interrater reliability, test-retest reliability, and concurrent validity (Nock et al., 2007).
676
677
678
679
680
681
682
683
684
685
686
687
688
689
690
691
692
693
694
695
696
697
698
699
700
701
702
703
704
705
706
707
708
709
710
711
712
713
714
715
716
717
718
719
720
721

671 6. Depressive Symptoms Index-Suicidality Subscale (DSI-SS): The DSI-SS (Metalsky & Joiner, 1997) will be used
672 to assess current suicidal ideation. The DSI-SS is a 4-item self-report measure of suicidal ideation that focuses
673 on ideation, plans, perceived control over ideation, and impulses for suicide. It is being used as a core measure
674 in the Military Suicide Research Consortium. Scores on each item range from 0 to 3, with higher scores
675 reflecting greater severity of suicidal ideation. Instructions will instruct the participants to respond based on the
676 past two weeks (for baseline and follow up visits) or the past week (for interim assessment visits). A systematic
677 review of measures of suicidal ideation and behaviors found that the DSI-SS had evidence of excellent internal
678 consistency and concurrent validity (Batterham et al., 2014).
679
680
681
682
683
684
685
686
687
688
689
690
691
692
693
694
695
696
697
698
699
700
701
702
703
704
705
706
707
708
709
710
711
712
713
714
715
716
717
718
719
720
721

671 7. The Clinician Administered PTSD Scale for DSM-5 (CAPS-5; Weathers, Blake, Schnurr, Kaloupek, Marx, &
672 Keane, 2012): The CAPS-5 is structured interview that assesses the DSM-5 criteria for PTSD (Weathers et al.,
673 2013). Each item is rated on a severity scale ranging from 0 (Absent) to 4 (Extreme/incapacitating) and
674 combines information about frequency and intensity for each of the 20 symptoms. Additional items that are not
675 included in the total score evaluate overall symptom duration, distress, impairment, dissociative symptoms, and
676 global ratings by the interviewer. Validation studies are nearly complete to establish the psychometric properties
677 of the CAPS-5 and findings will be reported in peer-reviewed publications. This interview is very similar to its
678 predecessor, the CAPS for DSM-IV, which has been considered the gold standard for evaluating PTSD and
679 demonstrated good reliability and validity (Weathers, Keane, & Davidson, 2001). In addition to reflecting
680 diagnostic changes for PTSD in DSM-5, the CAPS-5 differs from the CAPS in that frequency and intensity
681 ratings for each symptom are no longer scored separately, so the severity rating for each item determines
682 whether a symptom is present or not. Subscale scores are calculated by summing severity scores for items in
683 the following PTSD symptom clusters: re-experiencing, avoidance, negative alterations in cognitions and mood,
684 and hyperarousal. Scores ≥ 25 indicate a probable diagnosis of PTSD.
685
686
687
688
689
690
691
692
693
694
695
696
697
698
699
700
701
702
703
704
705
706
707
708
709
710
711
712
713
714
715
716
717
718
719
720
721

722 8. Life Events Checklist-5 (LEC-5): The LEC includes a list of 24 potentially traumatic life events commonly
723 associated with PTSD symptoms. The instrument was designed to facilitate the diagnosis of PTSD (Weathers,
724 Blake, Schnurr, Kaloupek, Marx, & Keane, 2013a).). In this study, the LEC-5 will also be used to identify the
725 index event and focus of the PTSD treatment. For each potentially traumatic life event, respondents rate their
726 experience of that event on a 5-point nominal scale (1 = happened to me, 2 = witnessed it, 3 = learned about it,
727 4 =part of my job, 5= not sure, and 6 = does not apply). Each nominal point will be scored separately, as either 0
728 (=not endorsed by participant) or 1 (=endorsed by participant).

729 9. PTSD CheckList-5 (PCL-5): The PCL-5 (Weathers, et al., 2010) is a 20-item self-report measure update of the
730 PCL designed to assess PTSD symptoms as defined by the DSM-5. The PCL-5 is currently available and has
731 been shown to have good psychometric properties. The PCL-5 evaluates how much participants have been
732 bothered by PTSD symptoms in the past month (for baseline and follow up assessments) or the past week (all
733 interim assessments) as a result of a specific life event. Each item of the PCL-5 is scored on a five point scale
734 ranging from 0 "not at all") to 4 ("extremely").

735 10. Deployment Risk and Resiliency Inventory-2 (DRRI-2) Combat Experiences subscale and DRRI-2 Postbattle
736 Experiences subscales:: The DRRI-2 (Vogt, et al., 2013) is a suite of 17 individual scales that assess key
737 deployment-related risk and resilience factors with demonstrated implications for veterans' long-term
738 health. The Combat Experiences and Postbattle Experiences subscales will be used to assess stressful
739 deployment experiences.

740 11. Monetary-Choice Questionnaire (MCQ): The MCQ (Kirby et al., 1999) is a 27-item self-administered
741 questionnaire. For each item, the participant chooses between a smaller, immediate monetary reward and a
742 larger, delayed monetary reward. The measure is scored by calculating where the respondent's answers place
743 him/her amid reference discounting curves, where placement amid steeper curves indicates higher levels of
744 impulsivity.

745 12. Suicide Cognition Scale Short Form (SCS-S): The SCS-S is a 9-item self-report measure designed to assess
746 suicide-specific thoughts and belief, with demonstrated reliability and validity with chronic pain patients (Bryan et
747 al., 2016). The SCS-S evaluates how much an individual agrees with the suicide-related cognition. Scores on
748 each item range from 1-5, with higher scores reflecting greater severity.

749 13. Posttraumatic Cognitions Inventory (PTCI): The PTCI is a 36-item questionnaire that was developed to
750 determine how an individual views the trauma and its sequelae in an attempt to understand both how PTSD
751 develops and is maintained (Foa, Elhers, Clark, Tolin, & Orsillo, 1999). Using an emotional processing theory,
752 Foa and her colleagues (1999) have suggested that PTSD is a consequence of disruptions in the normal
753 processes of recovery when an individual has excessively rigid concepts about self and world rendering the
754 person vulnerable if a traumatic event occurs. Thus the PTCI was developed as a measure of trauma-related
755 thoughts and beliefs. It is comprised of three subscales (Negative Cognitions about the Self, Negative
756 Cognitions about the World, and Self-Blame). The measure was tested in almost 600 adult volunteers recruited
757 from two university PTSD treatment clinics as well as a university community. Approximately 65% (n=392) of
758 individuals reported having experienced a trauma in which their own life or that of another person was perceived
759 to be in danger and their response at the time included intense terror, horror, or helplessness (Criterion A event).
760 The remaining 35% (n=162) denied such a traumatic experience. Of those who had experienced a trauma, 170
761 had PTSD symptoms of at least moderate severity while the remaining 185 reported a low symptom severity.
762 The three subscales of the PTCI demonstrated internal consistency with alpha coefficients ranging from 0.86 to
763 0.97. Convergent validity was demonstrated comparing the PTCI to appropriate subscales of the World
764 Assumptions Scale and Personal Beliefs and Reactions Scale. Significant correlations between the appropriate
765 subscales ranged from 0.20 to 0.85. The PTCI was able to differentiate individuals with and without PTSD
766 demonstrating discriminant validity (sensitivity = 0.78, specificity = 0.93). Test-retest reliability for each of the
767 three subscales at a 1-week interval ranged from 0.75 to 0.89 and for a 3-week interval ranged from 0.80 to
768 0.86.

769 770 771 772 773 774

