24 assessed at pre-treatment, post-treatment, and then 1- and 4-months after treatment completion.

25 3. OBJECTIVES/SPECIFIC AIMS/RESEARCH QUESTIONS

26 **Purpose:** The purpose of this randomized controlled trial (RCT) is to evaluate the efficacy of five 60-minute sessions
27 of Written Exposure Therapy for Suicide (WET-S) + Treatment as Usual (TAU) compared with TAU in high-risk,
28 suicidal service members, veterans, and DEERS eligible beneficiaries with posttraumatic stress disorder (PTSD) or
29 posttraumatic stress symptoms (PTSS).

30 42. Research Aims and Hypotheses:

31 Aim 1: Determine if Written Exposure Therapy for Suicide (WET-S) reduces the presence, frequency, and severity of
32 suicidal ideation, suicide plans, suicide gestures, suicide attempts, non-suicidal self-injurious behaviors, and re-
33 hospitalization for suicidality measured by the Self-Injurious Thoughts and Behaviors Interview (SITBI; Nock et al.,
34 2007) among service members, veterans, and DEERS eligible beneficiaries admitted to an acute psychiatric
35 inpatient unit for suicidal ideation (SI) and/or attempt with posttraumatic stress disorder (PTSD) or posttraumatic
36 stress symptoms (PTSS) compared with Treatment as Usual (TAU).

37 Hypothesis 1. Compared with TAU alone, WET-S + TAU will result in significantly greater reductions in
38 suicide-related outcomes pre-treatment to 1- and 4-months follow-up.

39 Aim 2: Determine if Written Exposure Therapy for Suicide (WET-S) reduces posttraumatic stress symptoms (PTSS)
40 severity measured by the Clinician Administered PTSD Scale for DSM-5 (CAPS-5; Weathers, Blake, Schnurr,
41 Kaloupek, Marx & Keane, 2013) among service members, veterans, and DEERS eligible beneficiaries admitted
42 to an acute psychiatric inpatient unit for suicidal ideation (SI) or attempt and posttraumatic stress disorder (PTSD) or
43 PTSS compared with Treatment as Usual (TAU.)

57 Hypothesis 2. Compared with TAU alone, WET-S + TAU will result in significantly greater reductions in
58 PTSS severity from pre- to post-treatment, 1- month, and 4-month follow-up.

59
60 Aim 3: Determine if reductions in posttraumatic stress symptoms (PTSS) severity mediate the association between
61 treatment condition and suicide-related outcomes (suicidal ideation, plans, gestures, attempts, non-suicidal self-
62 injurious behaviors, and re-hospitalizations) measured by the Clinician Administered PTSD Scale for DSM-5 (CAPS-

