Interviews and self-report measures

182
183
184
185
186

4-Month Follow-Up Assessment
Interviews and self-report measures

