7. RESEARCH PLAN

7.1 Selection of Subjects

- Target enrollment (number consented): 140
- Target number randomized: 124

7.1.1. Subject Population. Active duty military service members and veterans admitted to the CRDAMC inpatient psychiatry unit for treatment for suicidal thoughts or behaviors and PTS. The study will use a continuous enrollment process to allow for maximum flexibility in meeting individual patient/participant scheduling needs. Active duty service members will have priority for being enrolled in the study.

197

7.1.2. Source of Research Material. Interviews, self-report questionnaires, medical record review.

198

7.1.3. Inclusion and Exclusion Criteria.

Inclusion Criteria

1. Active duty military service member, veteran, or and DEERS eligible beneficiary (age 18- 65 years) hospitalized at Carl R Darnall Army Medical Center (CRDAMC) for non-suicidal self-injury, suicide thoughts, suicide plan or attempt confirmed by CRDAMC inpatient admission documentation.
2. PTSS of at least moderate severity (total scores > 20) confirmed by the CAPS-5.
3. Speak, read, and write English.

208

Exclusion Criteria

1. Active psychosis.
2. The presence of moderate to severe cognitive impairment (as determined by the inability to comprehend the baseline screening questionnaires).
3. The presence of any clinically significant factor that may impair an individual's ability to comprehend and effectively participate in the study, e. g., the presence of extreme agitation or violent behavior.

215

7.1.4. Description of the Recruitment and Prescreening Process. Under a waiver HIPAA Authorization for screening, study staff will collaborate with CRDAMC staff to identify potential participants who have been admitted for suicide thoughts and/or suicidal behaviors and that have symptoms of PTS as documented as part of the admission assessments.

220

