360 expectations in this yet unstudied population, we powered the study to detect small to medium sized effects for the group
361 by time interaction. Power was estimated using Repeated Measures and Sample Size computer software, accessible at
362 <https://rmass.org>. Assuming subject level randomization, a quadratic design matrix for the time effect, a 1-tailed alpha
363 level of .05, desired power of .80, equal sized treatment groups at baseline, an overall expected 15% attrition rate, a
364 stationary AR1 error correlation matrix starting at a modest $r = .30$, and desire to be able to detect at least a conventional
365 small to medium sized effect ($d = .35$) at the final assessment, the desired total sample size we intend to recruit is $N = 124$
366 ($n = 62/\text{group}$), a feasible recruitment goal given the targeted population.
367

368 **7.4.2 Primary (i.e., primary outcome variables) and secondary endpoints.** The primary dependent variables for suicidality
369 are the Self-Injurious Thoughts and Behaviors Interview (SITBI) interview and the Depression Symptom Index-Suicidality
370 Subscale (DSI-SS) self-report. The primary dependent variables for PTS symptoms and PTSD are the Clinician
371 Administered PTSD Scale (CAPS-5) interview and the PTSD CheckList-5 (PCL-5) self-report. Secondary endpoints
372 include associated psychopathology (severity scores on measures of depression, general anxiety, anger, and PTSD-
373 related cognitions)
374

375 **7.4.3 Data Analyses.** To examine hypothesis 1 (determine if WET-S + TAU reduces presence (past month), frequency,
376 and severity of suicidal ideation, suicide plans, suicide gestures, suicide attempts, and non-suicidal self-injurious
377 behaviors and re-hospitalizations related to suicidality relative to TAU only and hypothesis 2 (determine if WET-S + TAU

378 reduces PTS symptom severity relative to TAU only) , we will conduct intent-to-treatment (ITT) analyses including all
379 randomized participants who attend at least the first therapy session. General or Generalized Linear Mixed Effects
380 models, depending on the nature of the specific outcome, will be implemented for the primary ITT randomized
381 comparison of total CAPS-5 scores as well as SITBI variables of interest and number of subsequent inpatient
382 hospitalizations for suicidal behavior. The planned statistical design includes fixed effects for treatment (between-

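### The SITBI recall instruction is lifetime with no split by visit, while 7.4.3 analyses past-month presence; if applied at follow-up, it cannot yield the reduction that Hypothesis 1 states

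*Combined protocol and SAP*

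**What the plan says.** Section 7.4.2 states that the primary variables for suicidality "are the Self-Injurious Thoughts and Behaviors Interview (SITBI) interview and the Depression Symptom Index-Suicidality" Subscale (DSI-SS). For the SITBI, the only recall instruction in the available text is in Section 15.0, item 5: the Independent Evaluator will instruct "participants to answer the questions based on their entire lifetime of experience". It does not separate baseline from follow-up.

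Section 7.4.3 describes the Hypothesis 1 outcome differently. The purpose there is to "determine if WET-S + TAU reduces presence (past month), frequency" and severity of ideation, plans, gestures, attempts and non-suicidal self-injury. The one-month qualifier is attached to presence alone. The mixed models then serve the randomized "comparison of total CAPS-5 scores as well as SITBI variables of interest and number of subsequent inpatient" hospitalizations, with the group-by-time interaction as the effect of interest.

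Hypothesis 1 (Section 3) predicts greater reductions in "suicide-related outcomes pre-treatment to 1- and 4-months follow-up". The Abstract says participants are "assessed at pre-treatment, post-treatment, and then 1- and 4-months after treatment completion". Figure 1 lists "Interviews and self-report measures" at both the 1-month and the 4-month assessment, and self-report only at post-treatment.

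Other entries in Section 15.0 do give windows by type of visit. The DSI-SS (item 6) uses two weeks at baseline and follow-up and one week at interim visits. The PCL-5 (item 9) uses one month and one week respectively.

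**The concern.** The recall window decides what the Aim 1 interview outcome is. A past-month answer describes current status and can improve. A lifetime answer describes history, and history cannot be undone by treatment.

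The population makes this acute. Inclusion criterion 1 requires hospitalization "for non-suicidal self-injury, suicide thoughts, suicide plan or attempt confirmed by CRDAMC inpatient admission documentation". If SITBI answers agree with the admission record, each participant's admitting behaviour is already positive over the lifetime at baseline. Evaluators work from the administration instruction, not from the analysis section. If they apply item 5 literally at follow-up, the data collected will not be the variable that 7.4.3 analyses. Aim 3 also takes its suicide-related outcomes from the SITBI, so the mediation analysis would inherit the problem.

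**Working it through.** The plan gives no figure on this point to reproduce. The check sets the passages side by side and then follows the lifetime rule through.

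**1. Windows as stated**

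| Measure or variable | Place | Window |
|---|---|---|
| SITBI, as administered | 15.0, item 5 | entire lifetime, no split by visit |
| SITBI presence, as analysed | 7.4.3 | past month |
| SITBI frequency and severity, as analysed | 7.4.3 | none stated |
| DSI-SS | 15.0, item 6 | 2 weeks; 1 week at interim visits |
| PCL-5 | 15.0, item 9 | 1 month; 1 week at interim visits |

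**2. What a lifetime answer can do over time, given consistent reporting**

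- Presence at follow-up = max(baseline, new event). With baseline 1, change = 0 whether or not there is a new event. With baseline 0, change = 0 or +1. No path gives −1.
- Count at follow-up = baseline count + new events, so change = new events, which is never below 0.

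**3. Illustration for presence.** The documents give no rates, so these are assumptions. Take participants who endorse ideation at baseline (100%).

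| Past-month ideation at 4 months, TAU vs WET-S + TAU | Past-month change, in points | Difference | Lifetime change | Difference |
|---|---|---|---|---|
| 60% vs 35% | 60 − 100 = −40; 35 − 100 = −65 | −25 | 0; 0 | 0 |
| 80% vs 40% | 80 − 100 = −20; 40 − 100 = −60 | −40 | 0; 0 | 0 |

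The lifetime columns do not depend on the assumed rates.

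**4. Illustration for counts.** A simulation used 62 per arm, 2,000 runs, and assumed mean new events of 0.30 (TAU) and 0.10 (WET-S + TAU). The smallest individual change in a lifetime count was 0. Mean change was +0.30 and +0.10. Both arms rise. The arms differ by 0.30 − 0.10 = 0.20 new events per participant, but neither shows a reduction.

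**5. Can past-month status be recovered?** Subtracting successive lifetime counts gives new events over the whole interval. Between the 1-month and 4-month interviews that is 4 − 1 = 3 months, not the past month. At baseline there is no earlier interview to subtract. For presence already positive at baseline, subtraction always gives 0.

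**The case against.** The strongest reply is that the conflict is one of wording. Section 7.4.3 names a past-month window, Section 15.0 gives short descriptions of instruments rather than administration manuals, and the form may hold separate past-month items. In addition, the copy reviewed lacks the printed lines 287 to 319, which fall between Section 7.2 and the data-security text, as well as part of Figure 1. Assessment details by visit could sit there. This stands as a limit: it can only be said that the available text does not reconcile the two statements. It does not remove the conflict. Item 5 as written instructs a lifetime answer for a primary measure, and 7.4.3 leaves frequency and severity without a window.

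A second reply is that the group-by-time interaction needs a difference in change, not a fall. That is right. A reader might infer that a lifetime SITBI could show no treatment effect at all, and the documents do not support this. Lifetime counts can rise less in one arm, and a behaviour absent at baseline can newly appear in fewer participants. What is lost is the reduction from pre-treatment, and all movement in behaviours already endorsed.

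Other stronger readings also fail:

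- The plan defines no composite of any suicidal behaviour, so a guaranteed 100% ceiling on one would not describe a planned analysis.
- The protocol does not say that severity is a worst-point rating; an average-severity rating over the lifetime could fall.
- Past-month windows at 1 and 4 months leave some of the follow-up unobserved. That is a feature of the window and not part of this error.

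Finally, the DSI-SS is also primary and has clear windows. It covers ideation, plans, perceived control and impulses, so it limits the damage. It does not replace the SITBI for attempts, gestures or self-injury.

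**Conclusion.** Wrong as written, with moderate confidence. Section 15.0, item 5, and Section 7.4.3 give different windows for a primary outcome, and frequency and severity have none in 7.4.3.

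The size is categorical rather than numerical. Under the lifetime instruction, within-person change is exactly 0 for the presence of any behaviour endorsed at baseline and never below 0 for counts, at any event rate. The SITBI would be left with new events only.

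This rests on three assumptions: that the instruction is followed at the 1- and 4-month interviews, that the form has no separate past-month items, and that reporting is consistent across visits. The first two cannot be checked from the available text, and the wording of 7.4.3 suggests that a current window was intended. The DSI-SS and the count of subsequent hospitalizations are unaffected.

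**What to change.** Reconcile Section 15.0, item 5, with 7.4.3 by stating the SITBI window by visit and by variable:

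- Restrict the lifetime instruction to baseline, for description of the sample.
- Ask past-month presence, frequency and severity at baseline and at each follow-up SITBI interview, so that change from pre-treatment compares like with like.
- Name the same window in 7.4.3 for presence, frequency and severity.

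If the form already holds past-month items, item 5 should say so, and only the wording changes. Otherwise the cost is wording in two sections, the evaluator's script and a few questions per interview, with no added visits. This has to be settled before data collection, because lifetime-only answers cannot be converted later. A question about events since the previous interview is optional and is not needed to correct the conflict.
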